7. STUDY POPULATION AND RECRUITMENT

Describe who and how many subjects will be invited to participate. Include age, gender and other pertinent information.

We will recruit 22 (males and females) with a unilateral (i.e. single limb), transtibial (i.e. below-the-knee) amputation through the UD Amputee Clinic, Independence Prosthetics-Orthotics, Inc., and from the local community using fliers (uploaded), print advertisements (uploaded), and Consent-to-Contact forms (uploaded). Given the prevalence of amputations is greater in males, we expect that the sample will be predominantly male, but we will have no inclusion/exclusion criteria related to sex. Specifically, patients with unilateral transtibial amputations who receive services at Independence Prosthetics-Orthotics, Inc. or through the UD Amputee Clinic will be supplied a Consent-to-Contact form. This form will include contact information (first and last name; telephone numbers; best time to call) that will be faxed/mailed/placed in a folder for [name] if they are interested. [name] will facilitate a phone screening of the individual after supplying the participant with additional study information (see verbal recruitment script). Information from individuals who are ineligible or who opt not to participate after the phone screen or after receiving additional study information will be shredded.

We will also contact individuals with unilateral transtibial amputations who have previously signed consents to be re-contacted for research purposes while receiving services at the University of Delaware Physical Therapy Clinic. We will utilize the verbal script for recruitment (uploaded) in these cases.

20 controls will be recruited as age-, sex-, and body mass index-matched controls.

Telephone screening will be used to determine preliminary eligibility and information will be reviewed on-site (telephone screen uploaded).

Inclusion Criteria: All Participants

1. *English-speaking and -reading:* Due to lack of feasibility of conducting evaluation in other languages.
2. *Ages 18-60 years:* Adults > 60 years may have age-related changes in energy expenditure with walking. Children under 18 years may still be experiencing limb growth and maturation that effect walking.
3. *Saltin-Grimby Physical Activity Level⁴⁷ of I or II:* Goal is to sample individuals who are sedentary rather than presently active.

Inclusion Criteria: Individuals with Below-the-Knee Amputations

1. *Below-the-knee amputation:* Individuals with above-the-knee amputations are known to expend greater energy when walking than those with longer residual limbs.
2. *Currently wearing a prosthesis with use of an assistive device no greater than a cane:* Necessary for proposed testing.
3. *Wearing prosthetic at least 8 hours per day and inside and outside the home:* This criteria will help to ensure that we capture adults who are beyond the initial weaning into a prosthetic and who are prosthetic users rather than nonusers.

Inclusion Criteria: Controls

1. *Pain-free in the legs and low back regions:* Pain in these regions could be a confounding variable for the proposed testing.
2. *Walk without assistive device:* Goal is to capture able-bodied individuals for comparison

purposes.

Attach all recruitment fliers, letters, or other recruitment materials to be used. If verbal recruitment will be used, please attach a script. Uploaded

Describe what exclusionary criteria, if any will be applied.

Exclusion Criteria: All Participants

1. *Current infections/illnesses*: May affect O2 consumption with walking, physical activity, and/or performance testing.
2. *Significant cardiovascular, neurological, or pulmonary condition*: Such conditions may affect O2 consumption, physical activity, and/or performance testing.
3. *Uncontrolled blood pressure or diabetes*: It may not be safe for these adults to participate in exercise testing.

Exclusion Criteria: Individuals with Below-the-Knee Amputations

1. *Amputation of sound limb*: We will exclude individuals with bilateral amputations, which is a known contributor to increased energy expenditure and impaired balance.
2. *Current issues with residual limb affecting ability to walk or for which individual is receiving treatment (i.e. open skin lesion, physical therapy for initial gait training with new prosthetic) or has weight-bearing restriction*.

Describe what (if any) conditions will result in PI termination of subject participation.

Termination of participation would only occur under a circumstance in which it became clear that the participant could not participate in a safe manner, such as unstable or abnormal vital signs or significant balance impairments resulting in questionable safety, particularly with balance testing, physical performance testing, or treadmill testing.

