Hypothesis: Energy expenditure will be greater among inactive adults with a single, below-the knee amputation who demonstrate greater side-to-side differences in walking pattern during treadmill walking at both self-selected and fast walking speeds ($p<0.05$).

Specific Aim 7: Compare side-to-side differences in walking pattern (e.g. speed, step length, and joint position) between inactive adults with a single, below-the-knee amputation (n=20) and age-matched controls (n=20) during over-ground and treadmill walking using the APDM Mobility Lab software.

Hypothesis: For both over-ground and treadmill walking conditions, inactive adults with a single, below-the knee amputation will demonstrate greater side-to-side differences in walking pattern compared to age-matched controls ($p<0.05$).

Specific Aim 8: Explore the relationship between inspiratory muscle endurance, as quantified by an individual's sustained maximal inspiratory pressure (SMIP), and energy expenditure among inactive adults with a single, below-the-knee amputation (n=20) during treadmill walking at self-selected and fast walking speeds.

Hypothesis: Energy expenditure will be greater among inactive adults with a single, below-the knee amputation who demonstrate decreased SMIP values (p<0.05).

Specific Aim 9: Compare differences in inspiratory muscle endurance (measured by sustained maximal inspiratory pressure, or SMIP) between inactive adults with a single, below-the-knee amputation (n=20) and age-matched controls (n=20) using the PrO₂ device.

Hypothesis: Inactive adults with a single, below-the knee amputation will demonstrate decreased SMIP values compared to age-matched controls (p<0.05).

Specific Aim 10: Compare differences in inspiratory muscle endurance (measured by sustained maximal inspiratory pressure, or SMIP) between inactive adults with a single, below-the-knee amputation who have low back pain compared to those who do not report pain.

Hypothesis: Inactive adults with a single, below-the knee amputation who experience low back pain will demonstrate decreased SMIP values compared to individuals with a single, below-the-knee amputation who do not have pain (p<0.05).

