Questionnaires completed by participants who opt not to participate in the study (i.e. do not complete the informed consent) or who are deemed ineligible on-site will be shredded and placed in the trash (or given back to the participant to take home). This information will not be retained by the research staff. Informed consent documents will be retained in a locked file available only to research personnel. Participants will be given a copy of the informed consent for their records. Individuals with lower-limb amputations will also be asked to sign a HIPPA form. A copy of this form will be given to these research participants with a lower-limb amputation. The HIPPA form will request that the participant agree to share their medical records to allow determination of their current prosthetic components, to control for this factor during the data analysis. Specifically, we would like to control for the type of foot, passive or active and the type of suspension system, as these factors may impact energy expenditure. Only the minimal necessary information to conduct the research will be requested.

Standardized On-site Evaluation. During the on-site evaluation, a trained research team member will conduct a standardized clinical examination that will include review of questionnaires, vital signs, body anthropometric measurements, and balance and physical performance testing. Demographics information including pain and socket fit comfort score will be recorded. Patients will be asked general questions about their amputation. In the event that such questioning results in an emotional response, the examiner will refrain from further questioning that may increase participant distress. Importantly, the PI will specifically train examiners in questioning with sensitivity and role-play how to handle various emotional responses during questioning. The physical examination will include

assessment of vital signs (i.e. heartrate, blood pressure, and respiratory rate) to ensure appropriateness for participation in balance and physical performance testing and assessment of height and weight for calculation of body mass index using a medical-grade scale.

1. Cumulative Illness Rating Scale (CIRS): An index of co-morbidity burden used to quantify comorbidities based on significance of the condition and medication use; co-morbidities are a known factor related to real-world walking.³⁷ Administration of the CIRS will take less than 8 minutes.

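### Only controls must be free of leg and low back pain, so the Aim 9 difference in SMIP mixes amputation with pain and cannot be attributed to amputation alone

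*Combined protocol and SAP*

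**What the plan says.** Section 7 (Inclusion Criteria: Controls) requires controls to be "Pain-free in the legs and low back regions" and gives the reason: "Pain in these regions could be a confounding variable for the proposed testing".

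The criteria for the amputation group contain no counterpart. The nearest is an exclusion for "Current issues with residual limb affecting ability to walk or for which individual is receiving treatment". It does not reach low back pain, pain in the sound limb, or residual-limb pain that neither affects walking nor is under treatment.

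Section 5 sets two hypotheses on sustained maximal inspiratory pressure (SMIP). Under Aim 9, the amputation group "will demonstrate decreased SMIP values compared to age-matched controls". Under Aim 10, amputees "who experience low back pain will demonstrate decreased SMIP values" relative to amputees without pain. Aim 8 expects lower SMIP to go with higher energy expenditure among amputees. Aim 3 compares energy expenditure between amputees and controls.

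Controls are matched on age, sex and BMI (sections 6 and 7). Section 10 plans MANOVA/MANCOVA for Aims 3 and 6 to 10 and names no covariate for them; age and residual limb length appear only as examples for Aims 4 and 5. Pain is collected: "Demographics information including pain and socket fit comfort score will be recorded" (section 6), and PROMIS-29 includes pain interference. Neither measure is assigned to the Aim 3 or Aim 9 analysis.

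**The concern.** An entry criterion removes a suspected confounder from one group and leaves it in the other. That does not control the confounder; it builds in an imbalance. Here the same protocol also predicts the direction of the confounder's effect on the outcome, and that direction is the one Aim 9 predicts for amputation.

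At stake is what a lower SMIP in the amputation group would mean. It could reflect limb loss, back pain among people with limb loss, or both, and the planned analysis cannot tell these apart. Treating pain as a consequence of amputation does not fully settle the matter. A total effect of amputation would need a comparator with the usual frequency of pain among inactive able-bodied adults, and these controls are selected to have none.

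**Working it through.** The documents give no power calculation, effect size or SD for Aims 3, 9 or 10, so there is no stated figure to reproduce. The check is a reading of the design, followed by an illustration.

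**Structure.** Let δ be the SMIP difference between pain-free amputees and controls, p the share of amputees with low back pain, and d the SMIP deficit that goes with that pain, in SD units. Controls have p = 0 by design. Then

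expected Aim 9 difference = δ − p × d.

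Aim 10 hypothesises d > 0, and comparing amputees with and without back pain presupposes p > 0. On those premises the difference is negative even when δ = 0.

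**Would adjustment for pain help?** Take the model mean = a + b × (amputee) + c × (pain). No control has pain, so c is estimated from amputees alone, and b is the pain-free amputee mean minus the control mean. Adjusting for the presence of pain therefore amounts to the restricted contrast. It would separate the two, but the plan does not name it.

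**Illustrative size.** Assumptions: δ = 0; p of 25%, 50% or 75%; d of 0.5, 0.8 or 1.0 SD; 20 versus 20 (the n in the aims; sections 6 and 7 recruit 22 amputees); unadjusted two-sided t-test at 0.05, ignoring the matching; 20,000 simulated studies per row.

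| p | d (SD) | Shift p × d (SD) | Proportion with p ≤ 0.05 |
|---|---|---|---|
| 25% | 0.5 | 0.125 | 6.8% |
| 25% | 0.8 | 0.20 | 8.6% |
| 25% | 1.0 | 0.25 | 10.4% |
| 50% | 0.5 | 0.25 | 11.8% |
| 50% | 0.8 | 0.40 | 21.0% |
| 50% | 1.0 | 0.50 | 29.2% |
| 75% | 0.5 | 0.375 | 20.4% |
| 75% | 0.8 | 0.60 | 43.4% |
| 75% | 1.0 | 0.75 | 59.8% |

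Comparing only the pain-free amputees with controls gave 4.6% to 5.2% in every row.

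**Price of restricting.** The standard error ratio at 10 versus 20 against 20 versus 20 is √(1/10 + 1/20) / √(1/20 + 1/20) = √(0.15/0.10) = 1.22. The difference detectable with 80% power rises from 0.91 SD (20 versus 20) to 0.99 SD (15 versus 20), 1.12 SD (10 versus 20) or 1.46 SD (5 versus 20). A true difference of 0.91 SD has 80% power at 20 versus 20 and 62% at 10 versus 20.

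**Aim 3.** Aim 10 concerns SMIP and is silent on energy expenditure. Two indirect links remain: the control criterion is justified by reference to the testing as a whole, and Aim 8 ties lower SMIP to higher energy expenditure.

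**The case against.** The best defence is that Aim 9 is worded as a comparison of groups and does not claim a cause. If back pain lowers SMIP in some amputees, the group means really do differ, and rejecting equality is correct. This stands. A reader might take the table above as evidence that the type I error of Aim 9 is inflated. The documents do not support that: the percentages are error rates only for the claim that amputation itself lowers SMIP, and every input on pain is assumed.

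A pain-free, able-bodied comparator is also a legitimate choice, and sections 5 and 7 describe the controls as able-bodied. That stands too, provided the result is described as a difference from such adults.

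The plan does not ignore pain. Aim 10 splits amputees by back pain, section 6 intends to relate breathing endurance to pain, and MANCOVA leaves room for a covariate. But Aim 10 compares amputees only with each other and leaves the Aim 9 contrast unchanged, and no covariate is named.

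Finally, the protocol says that pain could confound the testing. It does not assert that it does, and a one-line reason for an entry criterion is not a causal model. The concern needs no more than that: the asymmetry between the groups is in the criteria, and the expected effect on SMIP is in Aim 10.

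**Conclusion.** The concern holds for Aim 9. By the protocol's own premises, the contrast of all amputees with controls combines amputation with pain and cannot be attributed to amputation alone. The direction of the shift follows from Aim 10's hypothesis. Its size cannot be established from the documents; 0.25 to 0.50 SD at 50% prevalence and a pain effect of 0.5 to 1.0 SD is an illustration.

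Two stronger readings go too far. One is that back pain accounts for the whole Aim 9 difference; nothing in the documents says how much it explains. The other is that Aim 3 has the same defect because Aim 10 predicts it; Aim 10 makes no prediction about energy expenditure, so for Aim 3 there is reason for a sensitivity analysis and no more.

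**What to change.** - Keep the all-amputee versus control contrast for Aim 9. Beside it, pre-specify a sensitivity contrast of amputees who meet the controls' criterion (no leg and no low back pain) versus controls, adjusted for age, sex and BMI because restricting the sample breaks matched pairs.
- Define the subset by leg pain as well as low back pain. Removing only low back pain would leave amputees with leg pain set against controls who have none. A three-level factor (controls, amputees without low back pain, amputees with it) can serve Aim 10.
- Run the same sensitivity contrast for Aim 3.
- Report estimates with confidence intervals for both contrasts. Do not require both to be significant; given the loss of power shown above, that rule could hide a real difference.
- If the difference shrinks materially in the restricted contrast, describe the all-amputee result as a difference from pain-free able-bodied adults, not as an effect of amputation itself.

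This changes analysis wording only; eligibility and recruitment stay as they are. Pain is already recorded, but the on-site form is not in the documents, so confirm that it captures leg and low back pain separately. The cost is a less precise sensitivity contrast (standard error about 22% larger at 10 versus 20, more if fewer amputees are pain-free) and the loss of some matched pairs.

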We will provide the first objective data that looks at the additional energy expenditure necessary for inactive adults with a lower-limb amputation who are using a prosthesis to walk short-distances as compared to able-bodied adults; this data may be used for the development of future prosthetic components that reduce energy expenditure. We will explore factors that may be linked to energy expenditure and physical activity among adults with and without a lower-limb amputation.

Specific Aim 1: Evaluate reliability and validity of physical activity self-report measures (i.e. International Physical Activity Questionnaire, Incidental and Planned Exercise Questionnaire-past week^{23,24}) as compared to physical activity characteristics obtained via step activity monitors (i.e. time spent walking/day, walking bout duration, walking bouts/day) among inactive adults with a single-limb amputation (n=20).

Hypothesis: *H1a: Both self-report measures will have excellent test-retest reliability (ICCs $\geq .75$). H1b: At least 1 self-report measure will demonstrate validity with ≥ 2 physical activity characteristics.*

Specific Aim 2: Determine what gait speed (mph) and cadence (steps/minute) constitute 3 METs, i.e. moderate-intensity activity, among inactive adults with a single, below-the-knee amputation during over-ground and treadmill walking (n=20).

Hypothesis: *H2a: 3 METs will occur at slower speeds during treadmill walking as compared to over-ground walking. H2b: 3 METs will occur at slower cadences during treadmill walking as compared to over-ground walking.*

Specific Aim 3: Evaluate differences in energy expenditure based on oxygen consumption between inactive adults with a single, below-the-knee amputation (n=20) and matched controls (n=20) during short bouts of over-ground and treadmill walking at self-selected gait speeds, 75% and 125% of self-selected gait speeds.

Hypothesis: *H3: Energy expenditure will be significantly greater at all walking speeds for adults with a limb amputation as compared to controls (a) over-ground and (b) during treadmill walking ($p \leq 0.05$).*

Specific Aim 4: Explore modifiable factors that may impact energy expenditure (assessed via oxygen consumption) including comorbidities, fatigue, sleep disturbance, balance, functional lower extremity strength, functional mobility, and agility among adults with (n=20) and without a unilateral below-the-knee amputation (n=20).

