Hypotheses: For both adults with and without a below-the-knee amputation (after controlling for covariates):

H4a: Comorbidities: Energy expenditure will be significantly greater at all walking speeds and for both walking conditions (over-ground and treadmill) for adults with greater comorbidity burden as assessed with the Cumulative Illness Rating Scale.

H4b: Fatigue: Energy expenditure will be significantly greater at all walking speeds and for both walking conditions (over-ground and treadmill) for adults who indicate fatigue on the PROMIS-29, as compared to those who do not indicate fatigue.

H4c: Sleep Disturbance: Energy expenditure will be significantly greater at all walking speeds and for both walking conditions (over-ground and treadmill) in adults who indicate sleep disturbance on the PROMIS-29, as compared to those who do not indicate sleep disturbance.

H4d: Balance: Energy expenditure will be significantly greater at 125% of self-selected gait speed for treadmill walking in individuals with balance deficits, as indicated by decreased Functional Reach Test distance and decreased time until loss of balance during the modified Clinical Test of Sensory Integration in Balance conditions 3 and 4 (foam, eyes open and foam, eyes closed).

H4e: Functional Lower Extremity Strength: Energy expenditure will be significantly greater for self-selected and 125% of self-selected walking speed for both walking conditions (over-ground and treadmill) in adults with decreased functional lower extremity strength, defined as slower 5 Times

Repeated Chair Rise times.

H4f: Functional Mobility: Energy expenditure will be significantly greater at for walking at 125% of self-selected speed for both walking conditions (over-ground and treadmill) in adults with decreased functional mobility, defined as increased L-test time.

H4g: Agility: Energy expenditure will be significantly greater for walking at 125% of self-selected speed for treadmill walking in adults with agility deficits, defined as slower Four Square Step Test times and Figure-of-8 Walk Test times.

We expect that relationship may be stronger among adults with a unilateral below-the-knee amputation, but we are not powered to explore between-group differences. In fact, Aim 4 (and Aim 5) is (are) exploratory, and we are looking for trends in differences.

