6. PROCEDURES

Describe all procedures involving human subjects for this protocol. Include copies of all surveys and research measures.

Overview: We propose to conduct a cross-sectional study of 22 adults with a unilateral transtibial amputation as compared to 20 sex-, age- (+/- 5 years), and body mass index- (+/- 5 kg/m²) matched controls. This one-time session is projected to take ~ 2hours on-site at the University of Delaware on the STAR campus within the Department of Physical Therapy.

Once contact is made with potential participants, inclusion and exclusion criteria will be examined in 2 phases, first over the telephone using a structured questionnaire, and then on-site by a research team member to validate inclusion and exclusion criteria obtained by telephone. Prior to telephone screening, verbal consent will be obtained from the participant. The on-site screening will occur after individuals have signed the informed consent.

All Participants will complete a series of questionnaires that will be sent via a mailing packet prior to the on-site evaluation. Questionnaires will take about 30 minutes to complete. Questionnaires included in this Mailing Packet will be the:

1. Demographics Mailing Sheet: Will provide pertinent demographic information necessary for characterizing and matching participants (i.e. age, sex).
2. Medical History Checklist: We would like to have participants complete this questionnaire as it will improve the efficiency and accuracy of the Cumulative Index Rating Scale.⁵⁰ Further, it will alert the physical therapist to any relevant problems that should be consider during physical performance testing and when testing energy expenditure during the 2 walking conditions.
3. Medication Sheet: Medication review using this sheet prior to physical performance testing and testing of energy expenditure during the 2 walking conditions will enhance patient safety and allow for appropriate interpretation of vital sign responses. This sheet will also allow increased efficiency and accurate scoring for the Cumulative Illness Rating Scale regarding comorbidities.⁵⁰
4. Activities Specific Balance Confidence Scale (ABC): The ABC is a valid³² 16-item

questionnaire where individuals rate how confident they are that they will not lose their balance or become unsteady with various ambulatory activities on a 0-100% scale, where 0=no confidence and 100%=complete confidence.²⁷

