8. RISKS AND BENEFITS

List all potential physical, psychological, social, financial or legal risks to subjects (risks listed here should be included on the consent form).

In your opinion, are risks listed above minimal* or more than minimal? If more than minimal, please justify why risks are reasonable in relation to anticipated direct or future benefits.

*(*Minimal risk means the probability and magnitude of harm or discomfort anticipated in the research are not greater than those ordinarily encountered in daily life or during the performance of routine physical or psychological examinations or tests)*

Minimal risks to the subjects are expected. The risks of the testing might include soreness and a temporary increase in skin, muscle, or joint pain. A small risk of a fall during balance testing, physical performance testing, and walking assessments is present. Participants will be free to withdraw from participating in the study at any time if they are uncomfortable with any of the procedures. Although no other risks or changes in the existing minimal risks are anticipated, participants will be informed if any new information arises regarding risks of participation that may affect their decision to continue in the study.

What steps will be taken to minimize risks?

To minimize soreness risks, participants will be asked to complete the minimal number of trials necessary to familiarize individuals with the testing equipment and assessment procedures and obtain a valid test. For balance, physical performance, and walking tasks, participants will be

appropriately supervised by a research member trained in participant guarding to minimize fall risk. The PI will be available by phone during all data collections. The testing done within the context of this study is used on a daily basis in the clinical setting, except that patients typically do not receive assessment of O₂ consumption during walking.

Describe any potential direct benefits to participants.

Investigators will review results of blood pressure screening with each participant and review the results of each participants' functional performance testing. If the vital sign screening indicates a need for an immediate referral, the examiner will contact the primary care provider and the patient will not be eligible to participate in further testing. Participants will be given blood pressure screening and physical performance handouts to share with their medical providers.

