Specific Aim 1: To determine reliability, intra-class correlation coefficients (ICCs) with 95% confidence intervals (CIs) will be calculated to evaluate test-retest reliability of physical activity

questionnaires. To evaluate validity between the self-report questionnaire data and activity-monitor obtained data that is continuous (e.g. steps/day, total activity in minutes/day), we will use ICCs with 95% CIs. We will quantify the relationship between the self-report data and activity-monitor data using Spearman's correlation coefficients. Interpretation will be as follows: $p \leq .25$ =weak correlation, $p=.26\text{--}.49$ =low correlation, $p=.50\text{--}.69$ =moderate correlation, $p \geq .70$ =high correlation.

Specific Aim 2: We will use receiver operating characteristic (ROC) curves to determine the minimal speed and cadence that corresponds to an oxygen consumption value of 10.5 mL/kg/min (i.e. 3.0 METs), as this has been identified by the World Health Organization as 'moderate intensity' activity.¹⁰

Specific Aims 3 and 6-10: We will use a MANOVA/MANCOVA to evaluate between-group differences with follow-up ANOVAs/ANCOVAs as appropriate ($p \leq 0.05$).

Specific Aims 4/5: Regression models will be used to explore relationships between energy expenditure (or average daily step counts) and each of the modifiable factors of interest, while controlling for relevant non-modifiable covariates, e.g. age, residual limb length.

Reported

Dissemination of results will occur through conference presentations and manuscript publications in peer-reviewed journals.

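### The Aim 3 MANOVA would discard completed walking stages from anyone stopped for safety at a later stage; a mixed model would keep them

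*Combined protocol and SAP*

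**What the plan says.** Section 5 (Specific Aim 3) compares energy expenditure in inactive adults with a below-the-knee amputation against "matched controls (n=20) during short bouts of over-ground and treadmill walking at self-selected gait speeds, 75% and 125% of self-selected gait speeds". Two walking conditions at three speeds give six stage values per person. H3 expects a greater value in amputees at every speed, in (a) over-ground and (b) treadmill walking.

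Section 6 describes a "cross-sectional study of 22 adults with a unilateral transtibial amputation as compared to 20 sex-, age" and body-mass-index matched controls. The treadmill test goes through 75%, 100% and 125% of self-selected speed in that order, and the over-ground test goes from slow to brisk. The order of the two tests is randomised for amputees, and each control follows the order of the matched amputee.

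Section 7 ends participation where it becomes unsafe, for vital-sign reasons or for "significant balance impairments resulting in questionable safety, particularly with balance testing, physical performance testing, or treadmill testing". Section 8 adds that when the vital-sign screen calls for immediate referral, "the patient will not be eligible to participate in further testing".

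Section 10 states for Aims 3 and 6-10: "We will use a MANOVA/MANCOVA to evaluate between-group differences with follow-up ANOVAs/ANCOVAs as appropriate". It does not say whether the six stages enter one model or several, or how a missing stage is handled. Section 9 foresees partial completion, but only for payment.

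**The concern.** A MANOVA needs a complete outcome vector for each person. Someone who completes treadmill stages 1 and 2 and is stopped at stage 3 drops out of the multivariate model altogether. The over-ground values go too if both conditions share a model. Because the rule ends participation, a person randomised to the treadmill first may never walk the over-ground stages.

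The reasons for stopping, balance and vital signs, are not obviously unrelated to the energy cost of walking. The group analysed could therefore differ from the group measured. If more amputees than controls are stopped, and those stopped have higher energy cost, the Aim 3 difference shrinks at the slower stages as well, where the data were actually collected. A reader of the results could not separate a small true difference from the effect of stopping.

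**Working it through.** The documents give no stopping rate, effect size, SD or power figure, so there is no planned figure to reproduce. What follows is an illustration.

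**1. What is discarded.** Six values per person (2 conditions × 3 speeds). With all six in one MANOVA, one missing stage discards up to 6 − 1 = 5 observed values. With a separate treadmill model, it discards up to 3 − 1 = 2.

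**2. Bias at completed stages.** Assumed inputs:
- 20 per group, SD 1, and a true difference of 1.0 SD at each of three stages
- between-stage correlation 0.7
- m of 20 amputees stopped at stage 3, and no controls stopped
- a stopping tendency with correlation ρ to the person's mean energy cost over the stages; those with the highest tendency are stopped.

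Complete-case difference at any stage = 1 − ρ × c × Δ, where
- c is the correlation of one stage with the three-stage mean: √((1 + 2 × 0.7)/3) = √0.8 = 0.894
- Δ is the sum of the m largest expected normal order statistics of 20, divided by (20 − m): 3.275/18 = 0.182 for m = 2, 5.327/16 = 0.333 for m = 4, 6.662/14 = 0.476 for m = 6.

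| Stopped of 20 | ρ = 0 | ρ = 0.3 | ρ = 0.8 |
|---|---|---|---|
| 2 | 1.00 | 1 − 0.3×0.894×0.182 = 0.95 | 1 − 0.8×0.894×0.182 = 0.87 |
| 4 | 1.00 | 1 − 0.3×0.894×0.333 = 0.91 | 1 − 0.8×0.894×0.333 = 0.76 |
| 6 | 1.00 | 1 − 0.3×0.894×0.476 = 0.87 | 1 − 0.8×0.894×0.476 = 0.66 |

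Simulation gives 0.95-0.87 for 2 stopped and 0.87-0.67 for 6, which agrees to within 0.01. If ρ refers to the person's underlying level instead, c = √0.7 = 0.837 and the last cell is 1 − 0.8×0.837×0.476 = 0.68.

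**3. What keeping the completed stages does.** In a simulation with a true 1.0 SD difference, 10-30% of amputees stopped and ρ of 0.5-0.8, using every completed stage gave 0.99-1.01 at stages 1 and 2. Predicting the missing stage 3 from the completed stages gave 0.91-0.98.

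**4. Selection matters more than numbers.** This is a second illustration: true difference 0.8 SD, 22 amputees v 20 controls, two-sided 0.05, with the worst-balance amputees removed.

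| Removed of 22 | Power, random loss | Difference (power), balance-energy correlation 0.3 | Same, correlation 0.5 |
|---|---|---|---|
| 0 | 0.715 | 0.80 (0.71) | 0.80 (0.72) |
| 2 | 0.693 | 0.75 (0.64) | 0.71 (0.61) |
| 4 | 0.669 | 0.71 (0.57) | 0.65 (0.51) |
| 6 | 0.640 | 0.67 (0.50) | 0.59 (0.41) |

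Losing six at random costs about 0.07 of power (0.715 − 0.640). Losing the six with the worst balance costs 0.21 to 0.31 (0.71 − 0.50; 0.72 − 0.41).

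**The case against.** **Stops may be rare.** Section 6 bases the speeds on pilot data in 44 patients. From the pilot means, 125% of self-selected speed is 1.25 × 0.88 = 1.10 m/s (K3) and 1.25 × 1.16 = 1.45 m/s (K4), below the mean fast speeds of 1.15 and 1.53. Stages last 2.5 minutes with seated rest between them. Eligibility limits age to 60 and walking aids to a cane, and excludes significant cardiovascular, neurological and pulmonary conditions. This stands: 10-30% stopped is an assumption, and so is a lower rate in controls.

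**The direction is not known.** That poor balance raises energy cost is itself a study hypothesis (H4d). Treadmill speed is scaled to each person's own pace, so people with poor balance may walk slower and use less oxygen per minute. This stands too. Bias toward no difference is the illustrated case, not a certainty.

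**Deletion is not written into the plan.** H3 is split by condition, which suggests separate models, and follow-up ANOVAs run separately on each stage could use the available data. That limits the loss, but the plan does not say this will be done, and the multivariate test itself still needs complete vectors.

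**Some losses precede walking.** People removed at the vital-sign screen, or during balance and performance testing before the walking tests, have no stage values. Changing the Aim 3 model does nothing for them.

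**A stronger reading does not hold.** A reader might infer that the MANOVA also strips H4d and H4g of the people they concern, since H4d expects that "Energy expenditure will be significantly greater at 125% of self-selected gait speed for treadmill walking in individuals with balance deficits". Section 10 analyses Aim 4 differently: "Regression models will be used to explore relationships between energy expenditure (or average daily step counts) and each of the modifiable factors of interest". Someone stopped before 125% is missing there because the outcome is missing. If stopping depends only on measured balance and the relation is linear, the slope is not biased (0.30 stays 0.30 and 0.50 stays 0.50). At a true correlation of 0.3 in amputees, its standard error rises from 0.22 to 0.27, 0.31 and 0.37 with 2, 4 and 6 of 22 lost. The cost is mainly range and precision, in an aim that Section 5 calls exploratory. Stops driven by vital signs during exertion could also bias the slope.

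**Conclusion.** The concern holds for Aim 3. The named method discards completed stages when a later one is lost, and the protocol's own safety rule and slow-to-fast order make that pattern possible. A method that keeps those stages is readily available.

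The size is conditional. For a true 1.0 SD difference, the complete-case estimate is about 0.95 to 0.67 SD with 2 to 6 of 20 amputees stopped, no controls stopped and a stopping-energy correlation of 0.3 to 0.8. It is unbiased if nobody is stopped or if stopping is unrelated to energy cost. Nothing in the documents fixes either quantity, so it cannot be said that the Aim 3 result will be biased, only that the planned method is exposed to it. The point does not extend to H4d and H4g through the MANOVA, and it is no criticism of the safety rule.

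**What to change.** - Leave the safety rule unchanged.
- For Aim 3, replace the MANOVA/MANCOVA with a linear mixed model, which SPSS can fit. Use group, stage, walking condition and their interactions with group (including group by stage by condition) as fixed effects, and participant as a random effect. The interactions are needed so that H3 can be tested at each speed in each condition, and every completed stage contributes.
- On the on-site form, record for each stage whether it was completed, stopped or not started, with the reason. Report these counts by group, with people removed before any walking stage shown separately.
- Do not add a sensitivity analysis for H4d and H4g that ranks a safety stop as the worst energy cost. People would be stopped for poor balance, assigned the worst outcome and then tested for a balance-outcome association. In simulation with no true association and the 2 or 4 worst-balance of 22 stopped, false positives in the hypothesised direction rose from 2.6% to about 15% and 56-58%.

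The cost is a change of analysis wording and one form field per stage. The field should be in place at the visit, because reasons may not be recoverable later. The mixed model assumes that a lost stage is predictable from the stages completed, and it recovers nothing for people who never start walking.
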